4. STUDY DESIGN

4.1. DESIGN / STUDY TYPE

This is a pragmatic cluster randomised controlled trial. The unit of randomisation is the team. The teams are four of the five Adult Community Mental Health 'Core' Teams in SLHD (Table 1). Randomisation will be stratified by sector (Eastern and Western): One team from each sector will be randomised to the intervention group, the other team will be allocated to the comparison group. The comparison group Teams will receive the intervention after the 3-month data collection is complete.

As there are only two teams per sector in the study, randomisation will be done by a person independent from the study by flipping a coin.

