4.2. EXPECTED PARTICIPANT NUMBERS

We aim to recruit 500 consumers and expect 400 to remain in the study at 3-month follow-up (20% loss to follow up). Power calculation: Assuming 20% change in the frequency and quality of primary and preventative care received by participants, a sample size of 91 per group is required to detect a change from 30 to 50% in primary outcomes based on $\alpha = 0.05$, $1-\beta = 0.8$. Assuming a design effect due to clustering of 2, a total sample of 360 is required (180 in each group).

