8. STATISTICAL CONSIDERATIONS

8.1. SAMPLE SIZE OR POWER CALCULATION

We aim to recruit 500 consumers and expect 400 to remain in the study at 9-month follow-up (20% loss to follow up). Power calculation: Assuming 20% change, a sample size of 91 per group is required to detect a change from 30 to 50% in primary outcomes based on $\alpha = 0.05$, $1-\beta = 0.8$. Assuming a design effect due to clustering of 2, a total sample of 360 is required (180 in each group).

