Secondary data from GP records, and SLHD eMR data (including hospitalisations, ED visits and ambulatory care records, associated costs, documentation audit report and metabolic report) as well as information from SLHD Targeted Activity & Reporting System (STARS) will be obtained and merged with the consumer survey data within the SLHD by AI [name]/AI [name]. GP records will be used to answer research questions 1 and 2 – quantitative analysis is described above. SLHD's patient data from the eMR (including hospitalisation, ED visits, ambulatory data, documentation audit and metabolic monitoring) as well as information from STARS and cost information will be used to answer research questions 3 and 4. These analyses of the resulting combined and de-identified dataset are described below.

The merged SLHD administrative data (micro-level data) will be from a 6-month period post-intervention (May-October 2023, considering the intervention as having a shared care plan in Inca between May and June 2023) compared with the 6-month periods, a) pre-intervention (November 2022-April 2023) and b) in the previous year (May-October 2022, to check for seasonal effect). The data will be analysed as part of the healthcare cost component (in the larger health economic evaluation).

The healthcare usage (such as hospitalisations, ED visits, ambulatory care and GP care) data will firstly be grouped in a meaningful way e.g., for hospitalisations, summarised by ARDRGs, diagnoses and average length of stay. Costs will be summarised too e.g., for hospitalisation costs, these will be described in terms of main components such as 'Medical', 'Nursing' and 'Allied Health' costs occurring during admissions. We will calculate the total and mean utilisation of healthcare services and costs (and undertake further econometric analyses) for those in the SHAReD intervention, usual care, and combined (SHAReD and comparison) groups. These summary statistics (and later modelled estimates) will be included in the cost component of the economic evaluation.

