Additionally, it will be informative to measure the healthcare costs of SMI from the viewpoint of the SLHD/NSW health system, expressed as average total costs of SMI treatment per person under the alternative care situations. The SHAReD care group may be broken down into several subgroups for the analysis, and based on the degree to which they completed the intervention (e.g. their adherence to the shared e-plan, how many times they were engaged with the essential components

of the intervention and what they received, the quality of SHAReD care delivery, and participant acceptability and responsiveness to the intervention).²⁷ All costs will be expressed in 2023 Australian dollars.

Econometric methods commonly used to address issues associated with healthcare usage and cost variables such as problems of heteroscedasticity and skewness will be applied in this study.²⁸ These methods will be used to estimate the total (and differences in/incremental) costs (and costs specific to single and multiple health conditions, health risks, cardiometabolic outcomes) associated with the SHAReD care situation versus usual care adjusted for several participant and system-level characteristics. Various econometric methods will be explored such as log-transformed ordinary least squares models, GLMs (and may be those for repeated measures/panel data too) and survival (duration) models, with “goodness of fit” and other statistical measures used to make decisions about the models.²⁹

There may be missing data especially from the survey or general practice or as a result of merging data. This will be addressed by multiple imputation in the analysis.

To address confounding, variables with baseline differences between SHAReD intervention and usual care will be included in the final multivariate regression analysis.

To manage any risk that merging databases of non-identifiable data could subsequently result in the individuals being identified, data will be de-identified after combining the SLHD eMR data and costs with consumer survey data and stored securely (see section 12 of protocol). Only data with more than five individual responses will be released.

Costing component and the economic evaluation

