Health related quality of life will be collected using the EuroQol five dimensions, 5 levels questionnaire (i.e. EQ5D5L), which is a reliable and validated utility-based and disease-generic quality of life measure used for medical decision-making in Australia and elsewhere. The cost-effectiveness study will use QALYs gained as one of the main health effects based on the EQ5D5L questionnaires administered at baseline, during, and at completion of the trial. Factors for changes in the quality of life (including the various domains, visual analogue score, overall score and QALYs) of study participants over time will also be explored using a range of econometric methods, such as difference in difference models, generalised linear mixed models (GLMMs) for repeated measures /panel data and other panel data methods.

The effects of the SHAReD intervention on employment and other activities undertaken by participants (and costed out) will be examined using summary statistics and logistic/probit models.

The economic evaluation will apply established principles and methods for undertaking cost-effectiveness (and cost-utility) analyses, consistent with the National Health and Medical Research Council's (NHMRC) economic evaluation guidelines.³⁵

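### The econometric models that section 8.2 assigns to service use and costs carry no stated provision for team randomisation, in conflict with the plan's general multi-level statements

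*Protocol*

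**What the plan says.** Section 4.1 states: "The unit of randomisation is the team". There are four teams, one per arm in each of two sectors. Section 8.1 allows for clustering in the sample size: "Assuming a design effect due to clustering of 2, a total sample of 360 is required (180 in each group").

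The synopsis (Statistical considerations) and the quantitative analysis paragraph of section 8.2 both compare the arms with linear or generalised multi-level mixed models. Intra-class correlations for care coordinators, teams and GPs are to be examined before random effects are chosen. Neither statement is limited to particular research questions.

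Under Data combining and cost analyses, section 8.2 then divides the work by data source. GP records serve questions 1 and 2, with the analysis given earlier in the section. Hospital, ED and ambulatory records, "as well as information from STARS and cost information will be used to answer research questions 3 and 4", with the analysis given later. The later text reads: "Various econometric methods will be explored such as log-transformed ordinary least squares models, GLMs (and may be those for repeated measures/panel data too"), and continues with survival models. Choice among them rests on goodness of fit and other statistical measures. The stated purpose is to handle skewness and heteroscedasticity, with adjustment for participant and system-level characteristics.

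The economic evaluation text adds that effects on employment and other activities "will be examined using summary statistics and logistic/probit models".

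**The concern.** Assignment is by team, so the arm comparison contains between-team variation that individual-level standard errors do not capture. The routed text lists models that are individual-level by default and gives no team effect, cluster-robust variance or between-team degrees of freedom. Adjusting for system-level characteristics does not supply one, and choosing a model by fit does not look for the problem.

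The affected results include secondary endpoint 8 (ED attendances and hospitalisations), endpoint 17 (hospitalisation costs), and the service-use and cost parts of hypotheses 3 and 4. The synopsis plans significance tests on usage and cost data, and section 8.2 feeds modelled estimates into the economic evaluation. An ordinary difference between two pairs of teams could then be reported as admissions or costs avoided because of the online plan. Section 1.2 says a successful intervention will be rolled out, so such an error would have consequences.

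**Working it through.** **1. The plan's own figure.** Inputs from section 4.2: 30% versus 50%, alpha 0.05 (taken as two-sided), power 0.80; "a sample size of 91 per group is required to detect a change from 30 to 50% in primary outcomes".
- n = (1.960 + 0.842)² × (0.30 × 0.70 + 0.50 × 0.50) / 0.20² = 7.849 × 0.46 / 0.04 = 90.3, so 91 per group. This matches.
- 91 × 2 = 182 per group and 364 in total, against the stated 180 and 360. The difference is rounding.

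**2. Implied intra-class correlation.** With 360 / 4 = 90 consumers per team, and taking the team as the clustering level, 1 + (90 − 1) × ICC = 2 gives ICC = 1/89 = 0.0112.

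**3. Post-only arm contrast analysed at individual level.** The naive variance is too small by the design effect DE, so the true rate of a nominal 5% test is 2 × [1 − Φ(1.96 / √DE)].

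| Assumed DE | 1.96 / √DE | False-positive rate |
|---|---|---|
| 1.5 | 1.600 | 11.0% |
| 2 | 1.386 | 16.6% |
| 3 | 1.132 | 25.8% |

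Simulation of four teams (20,000 runs) at DE 2 gave 16.4% with 90 per team and 16.8% with 100 per team.

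**4. Change contrast.** Section 4.4 defines endpoints as between-arm differences in change, and section 7 compares a post window with earlier windows. A stable team effect cancels in a change. Let s be the correlation of a team's effect between windows, and assume a within-person correlation of 0.5.
- Team part of the change variance: B = 2 × (1/89) × (1 − s).
- Individual part: W = 2 × (1 − 1/89) × (1 − 0.5) = 0.989.
- Effective DE = (B + W/90) / [(B + W)/90].

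| s | B | Effective DE | Formula | Simulation |
|---|---|---|---|---|
| 1.0 | 0 | 1.00 | 5.0% | 5.0% |
| 0.8 | 0.0045 | 1.40 | 9.8% | 9.7% |
| 0.5 | 0.0112 | 2.00 | 16.6% | 16.8% |
| 0 | 0.0225 | 2.98 | 25.6% | 24.9% |

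**5. Team-level comparator.** A t test on the four team values, with 4 − 2 = 2 degrees of freedom, rejected in 4.7-5.0% of simulated null trials.

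**The case against.** The strongest reply is that the econometric text is silent on clustering and does not exclude it. Its list is open, panel versions are mentioned, and OLS and GLM describe a mean model, which can carry random effects or cluster-robust errors. The general multi-level statement sits in the same section and is not withdrawn. Variance estimation for cost models is also commonly left to a statistical analysis plan. All of this stands against one reading a reader might reach: that the protocol sets team randomisation aside. It does not say so. The reply does not remove the conflict, because section 8.2 itself sends questions 1 and 2 to one set of methods and the administrative data for questions 3 and 4 to another. Two analysts could follow the text faithfully and produce different standard errors.

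Three further inferences are not supported.
- **A single rate of about 16%.** The design effect of 2 was set for the binary primary outcomes with no clustering level named, and the planned contrasts are changes. The rate depends on both assumptions.
- **Logistic or probit models for service use and costs.** They are named only for employment and other activities, which are not listed endpoints.
- **Extra inflation from treating the three six-month windows as independent records.** The plan compares the post window with earlier ones. It does not average each arm over all three.

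The routing also does not cover all of question 3: health-risk measures from the consumer survey lie outside it, and GP visits come partly from GP records. Quality of life has mixed models among its listed methods, though for repeated measures. Descriptive reporting is already planned for the cost-consequence step, but that does not cover the planned significance tests.

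**Conclusion.** The point holds as an unresolved conflict in section 8.2, with a material consequence if the routed text is followed as written. Individual-level fitting would give a false-positive rate of about 16-17% for a post-only contrast at an assumed design effect of 2, with a range of 11% to 26% for design effects of 1.5 to 3. For a change contrast the rate would be about 5% to 25%. The low end requires team effects to be fully stable between windows, and the documents give nothing that would establish this. These figures assume four equal teams, an ICC of 1/89 and a within-person correlation of 0.5, and they apply only if clustering is in fact left out. The outcomes are secondary, so this should be corrected but does not threaten the primary comparison.

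**What to change.** In the cost-analysis part of section 8.2, state that every comparison of SHAReD with usual care on service use or costs must respect team randomisation, and reconcile that sentence with the synopsis and the quantitative analysis paragraph.

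- Use the pre and post windows through an arm-by-period term or a change score, and make repeated-measures handling a requirement.
- Base inference on team-level changes with a t reference on the between-team degrees of freedom, or on a GLM with team effects and small-sample degrees of freedom. With four teams, a team random effect alone does not guarantee a 5% error rate. State whether sector is fitted, since doing so reduces the between-team degrees of freedom from 2 to 4 − 3 = 1.
- Where the interval is too wide to be useful, report the estimate as descriptive, without a significance claim.
- Apply the same rule to the employment and activity models.

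The cost is a few sentences and some analysis time. Team membership and the windows are already part of the design, so no new data are needed. The price is wider intervals, and some service-use and cost contrasts will end up descriptive.

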

Statistical considerations
	
Sample size calculation Assuming 20% change, a sample size of 91 per group is required to detect a change from 30 to 50% in primary outcomes based on $\alpha = 0.05$, $1-\beta = 0.8$. Assuming a design effect due to clustering of 2, a total sample of 360 is required (180 in each group).
 
Analysis plan For analysis of differences between the intervention and usual care alternatives, linear or generalised multi-level mixed models will be estimated depending on the type of outcome in question. Intra-class correlations will be calculated to compare the amount of variance associated with design features as individual participants are nested within care coordinators who are nested within community mental health teams, and those same participants are also nested within GPs who may also be nested within medical centres, which will occur before selecting random effects for these models. As well as an analysis of completers, defined as those consumers, care coordinators and GP triads that complete an online shared care plan, an intention to treat (ITT) analysis will also be completed for this study. For the ITT analysis, those who have dropped out will be treated using a variety of sensitivity analyses. Further, baseline predictors and intervention features of both the SHAReD (e-shared care) and usual care situations will be added to multi-level models to identify effects of these characteristics on outcomes. Qualitative analyses (predominantly deductive but inductive coding will also be applied to detect new and emerging themes) will also be undertaken. All relevant costs such as implementation costs and healthcare usage [hospitalisations, GP care, specialists, allied health, and prescribed medication, and the multiple outcomes such as interactions with the health system, engagement, preventive tests undertaken, clinical measures and quality of life for participants in the intervention and usual care groups will be quantified, and tests of significance will be undertaken on these data. These results will be used in a cost-consequence analysis (CCA). A comprehensive within-trial cost-effectiveness study will also be conducted provided effectiveness has been demonstrated, with the main effects/benefits consisting of satisfactory completion of an online shared care plan, reduction in consumer cardiometabolic risk, and avoiding unplanned hospitalisations. A cost-utility evaluation will be conducted if effectiveness in relation to quality of life has been demonstrated, to provide a ranking of the alternatives (e-shared care, usual care) on the basis of the amount of resources (costs) used to gain an extra quality adjusted life year (QALY) by receiving the SHAReD intervention. All the necessary effects/benefits and costs (direct medical, consumer costs for medical care and any indirect costs) will be identified, counted and valued using established methods. A range of incremental cost-effectiveness ratios (ICERs) will be calculated such as the incremental cost for an extra QALY gained, cost for an unplanned hospitalisation that was avoided. Sensitivity analysis will be conducted and some results presentations graphically.

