patient data collection using medical record numbers (and eMR) and associated SLHD costings during the study. Costs attributable to the research will not be considered. Estimates of how the work of clinicians (and thus costs) has changed from the situation without the SHAReD intervention will also be explored during the focus groups. Variations in healthcare usage (such as hospitalisations and other medical treatment sought) and costs occurring later in the study (and up to 3 months post completion of the intervention) will be sought from SLHD eMR reports and the SLHD Performance Unit for cost of ED presentations and hospitalisations. The mean costs in the SHAReD intervention and usual care groups will be compared in addition to the mean health effects/benefits such as the care plan completion rate, quality of care received, clinical metrics, hospital admissions (and readmissions), hospital length of stay, and score on the utility-based and disease-generic quality of life measure (EQ5D-5L).^{30,31}

Having data on both the healthcare resource utilisation (costs) and health effects/benefits for the different groups will allow us to undertake a detailed cost-consequence analysis (CCA) – a first step for the economic assessment. CCA is a widely used form of economic assessment and recommended for reporting on health interventions with significant complexity and when there are multiple effectiveness measures such as programs/models of care seeking to address a range of clinical outcomes (Drummond et al 2005), and broad-reaching programs that have a range of health and non-health related effects needing to be quantified and assessed (NICE 2017). For this initial step of the economics work, the relevant costs and multiple outcomes will be calculated and presented in a disaggregated way which enables decision-makers to assess the relative importance of each component to the context they face. The comparator will consist of those consumers who did not receive the SHAReD intervention. Descriptive analysis will be used to estimate the total and mean costs (and standard deviations) associated with the intervention and usual care, as well as the effectiveness information (outcomes) and reported in a disaggregated manner.

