A within-trial economic evaluation of the SHAReD intervention compared to usual care will be conducted if effectiveness has been demonstrated. The mean costs and health effects/benefits will be used to generate the incremental cost for a one-unit improvement in the health effect of interest (e.g. an extra Quality Adjusted Life Year [QALY]) for the SHAReD group compared to the usual care group. We will assemble several ICERs such as the incremental cost for each care plan completed, the reduction in cases with cardiometabolic risk (and separate risk factors), unplanned hospital admissions avoided, and a gain in QALYs among the SHAReD group compared with the usual care group. The results of the evaluation will be used to determine the within-trial cost-effectiveness (and utility) of the SHAReD intervention i.e. whether it offered value for money.

The results will be shown graphically on a cost-effectiveness plane.³² Thus, the cost-effectiveness plane will show the differences in healthcare costs and health effects/benefits between the SHAReD intervention and usual care groups in two dimensions, with the healthcare costs plotted against health effects/benefits. We will use the bootstrap method, which is a re-sampling method used to estimate basic statistics on a population through sampling the dataset with replacement, to create 10,000 random samples and then use these samples to establish a statistical distribution for the costs and health effects/benefits (means and standard deviations) in the intervention and control groups, as well as to generate confidence intervals for the applicable ICER.³³ Various sensitivity

analyses will be undertaken. We will also generate a cost-effectiveness acceptability curve to summarise the impact of uncertainty on the results of the evaluation, expressed as the main ICER in relation to possible values of the cost-effectiveness threshold.³⁴ Values for thresholds will be determined by considering what is meaningful for the healthcare provider.

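### The cost per QALY is defined on group means, and baseline EQ-5D-5L is not fixed as a covariate for the incremental QALY

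*Protocol*

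**What the plan says.** All of this is in the Protocol; section 8.2 is the detailed analysis plan.

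- **The ratio.** Under the costing component and economic evaluation: "The mean costs in the SHAReD intervention and usual care groups will be compared in addition to the mean health effects/benefits", and then "The mean costs and health effects/benefits will be used to generate the incremental cost for a one-unit improvement in the health effect of interest". Cost per QALY is one of several ratios listed.
- **Its uncertainty.** The 10,000 bootstrap samples are used to "establish a statistical distribution for the costs and health effects/benefits (means and standard deviations) in the intervention and control groups". They also supply the interval for the ratio. No covariate is mentioned.
- **The QALY.** It is "based on the EQ5D5L questionnaires administered at baseline, during, and at completion of the trial", so the baseline value is part of the total.
- **Costs.** Under data combining and cost analyses, incremental costs are to be estimated with adjustment for participant and system characteristics. "These summary statistics (and later modelled estimates) will be included in the cost component of the economic evaluation".
- **Conditional adjustment.** The same part says that "variables with baseline differences between SHAReD intervention and usual care will be included in the final multivariate regression analysis". Section 5.4 (Confounders) also allows adjustment if it proves necessary. It lists demographic, socioeconomic and mental-health characteristics, and does not name utility.
- **Quality-of-life models.** Factors for change in the quality of life (QALYs included) of "study participants over time will also be explored using a range of econometric methods, such as difference in difference models" and mixed models.
- **A gate.** The synopsis says: "A cost-utility evaluation will be conducted if effectiveness in relation to quality of life has been demonstrated".

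**The concern.** A QALY total computed as an area under the utility curve contains the baseline utility. A baseline difference between arms therefore counts directly as QALYs gained or lost, and whatever part of it persists to follow-up counts again. Only four teams are randomised, two per arm, so balance on utility cannot be relied on.

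The adjustment text elsewhere does not settle the matter. The rule in the cost section and the rule in section 5.4 both depend on what imbalance is seen, and neither names utility. Modelled estimates are directed to the cost component only. The quality-of-life models are exploratory and are not said to feed the ratio, the cost-effectiveness plane or the acceptability curve. Costs could thus be adjusted and QALYs not, within one ratio. That ratio is meant to show whether the intervention was value for money, which is part of the fourth research question.

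**Working it through.** **The plan's own figures.** The protocol gives no figure for QALY precision, so the check borrows from its sample size. For 30% against 50%, two-sided α 0.05 and power 0.80: (0.3×0.7 + 0.5×0.5)×(1.960 + 0.842)²/0.2² = 90.3, so 91 per group, as stated. With design effect 2 this is 182 per group against the stated 180, a small rounding difference. Retention of 500×0.8 = 400 also reproduces, giving about 200 per arm.

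**Assumptions not in the protocol.** Utility SD s = 0.20 to 0.25; correlation ρ = 0.3 to 0.7; the design effect of 2, set for the primary outcomes, applied to utility; horizon T = 0.25 or 0.5 years.

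**1. How large a chance imbalance is plausible.** SE of the baseline difference = s·√(2×2/200) = 0.028 (s = 0.20) or 0.035 (s = 0.25). A difference of at least 0.05 in either direction has z of 1.77 or 1.41, hence probability 8% or 16%. For at least 0.03 the probability is 29% or 40%. Even 0.05 would usually not be flagged by a 5% significance test, so a rule triggered by a significant difference would miss it.

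**2. What it does to the QALY difference.** With two time points, QALY = T(U0+U1)/2. With no intervention effect, an imbalance b contributes T·b/2 directly and T·b·ρ/2 by carry-over, in total T·b·(1+ρ)/2. For b = 0.05:

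- T = 0.25: 0.25×0.05×1.3/2 = 0.008 at ρ 0.3, and 0.25×0.05×1.7/2 = 0.011 at ρ 0.7.
- T = 0.5: 0.016 and 0.021.

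For comparison, a true utility gain of 0.05 at follow-up gives T×0.05/2 = 0.006 (T = 0.25) or 0.0125 (T = 0.5).

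**3. Precision.** The unadjusted variance of a QALY is T²s²(1+ρ)/2. Given U0 it is T²s²(1−ρ²)/4. The variance ratio, adjusted to unadjusted, is (1−ρ)/2, whatever T, s, n or a common design effect. The SE ratio, unadjusted to adjusted, is √(2/(1−ρ)). The last two columns come from simulating four teams of 100 with design effect 2.

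| ρ | Variance ratio | SE ratio | Simulated SE ratio | Simulated, team effects uncorrelated over time |
|---|---|---|---|---|
| 0.3 | 0.35 | 1.69 | 1.68 | 1.52 |
| 0.5 | 0.25 | 2.00 | 2.02 | 1.57 |
| 0.7 | 0.15 | 2.58 | 2.61 | 1.59 |

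Example with s = 0.20, T = 0.5, ρ = 0.5: the 95% half-width is 0.024 QALY unadjusted and 0.012 adjusted.

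**4. With a mid-trial EQ-5D.** QALY = T(U0+2U1+U2)/4, with ρ = 0.5 between all pairs. Unadjusted variance is proportional to 6 + 10×0.5 = 11. Given U0 it is 4×0.75 + 0.75 + 4×0.25 = 4.75. The variance ratio is 4.75/11 = 0.43 and the SE ratio 1.52. The null shift falls from 0.75·T·b to (0.25 + 0.75×0.5)·T·b = 0.625·T·b.

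**5. If QALYs gained means change from baseline.** The variance ratio becomes (1−ρ²)/(2(1−ρ)) = (1+ρ)/2, that is 0.65, 0.75 and 0.85 at ρ 0.3, 0.5 and 0.7. The gain is smaller, and an imbalance then acts in the opposite direction, by −T·b·(1−ρ)/2.

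**The case against.** A reader might infer that the plan uses raw means and makes no adjustment at all. The text does not say so. It speaks of means without calling them unadjusted, and model-based means are not ruled out. Section 5.4, the cost section and the exploratory models all mention adjustment, and a difference-in-difference model would remove a baseline utility difference. What is missing is the link from any of these to the incremental QALY, together with a commitment that does not depend on the observed imbalance. Detail may sit in an analysis plan not shown. But section 8.2 does fix the estimator and the bootstrap, so the wording there is open to review.

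A reader might also infer that incremental costs are unadjusted. That is not supported, because adjusted cost models are planned and their estimates are directed to the cost component.

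A third tempting inference is that, with no true effect, baseline imbalance will decide the value-for-money conclusion. The gate in the synopsis largely stands against this: without a demonstrated quality-of-life effect no cost per QALY is produced. The gate does not protect the size of the QALY increment once the analysis is run. The synopsis also describes the team pairs as matched on service type and consumer population. That may reduce imbalance in utility but does not remove it.

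Finally, the gain in precision rests on values the protocol does not give, and it shrinks under the alternatives in steps 3 to 5 of the working. That stands, although every scenario examined shows some gain.

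**Conclusion.** The point holds as a gap in the stated estimator. The cost per QALY and its bootstrap are defined on group means, and nothing ties a baseline-utility term to the incremental QALY. If the cost-utility analysis is triggered, a chance baseline difference carries into the QALY difference at about T·b·(1+ρ)/2. The unadjusted SE is about 1.7 to 2.6 times the adjusted SE for ρ 0.3 to 0.7 with two time points. It is about 1.5 times with a mid-trial measure at ρ 0.5, and 1.5 to 1.6 times if team effects do not persist. If QALYs gained means change from baseline, the gain is smaller still.

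Utility SD, ρ and the design effect for utility are assumptions. The documents therefore do not support a flat statement that the interval will be far too wide. Nor does adjustment cure having two teams per arm: normal-theory widths understate the uncertainty of both estimators. The change is worth making because it is nearly free and protects a stated, though secondary and conditional, objective.

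**What to change.** In section 8.2, where the ratios and bootstrap are defined:

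- State that the incremental QALY is the arm coefficient from a regression of each consumer's QALYs on arm, baseline EQ-5D-5L utility and sector (the stratifier), with these terms always included whatever imbalance is seen.
- State that the adjusted incremental cost already planned feeds the same ratio, and that its model always includes the consumer's own cost in the pre-intervention period (November 2022 to April 2023), which the administrative extract covers.
- Refit both models in every bootstrap sample, so that the interval, plane and acceptability curve all use the adjusted differences.
- Report unadjusted means descriptively in the cost-consequence analysis.

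The cost is a few sentences and two regressions inside the bootstrap loop. No new data are needed. The small downside is that consumers without a baseline EQ-5D need imputing, for which the multiple imputation already planned can serve.
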